## BACKGROUND AND RATIONALE

When people die, it is normal for their bereaved family members (FMs) to experience grief. This grief usually diminishes, but in some cases FMs suffer from severe grief reaction (SGR) with intense yearning or separation distress, as well as emotional, cognitive and functional impairment lasting months or years. SGRs have been variously labelled as Complicated Grief (CG), Prolonged Grief Disorder (PGD), or Persistent Complex Bereavement-Related Disorder (PCBRD, included in the Diagnostic Services Manual ver. 5), and may also feature other psychiatric morbidity such as depression or post-traumatic stress disorder (PTSD). SGRs are linked with declining health, use of healthcare resources, and even death.

The COVID-19 pandemic has affected many aspects of end-of-life care, even for those who die of illnesses other than COVID-19. For those admitted to acute or long-term care, visitor restrictions have significantly impacted family presence in the final hours of life. Videoconferencing and telephone interactions are not feasible for many elderly or dying patients, and are not recommended when patients are actively dying. Supportive interactions from healthcare providers are also limited by infection control measures. COVID-19 can also enhance feelings of guilt; FMs may have unwittingly transmitted COVID-19 during a visit, or the FMs may feel guilt for not having taken them out of a Long-Term Care facility prior to an outbreak. All of these factors will likely increase the risk of SGR. Moreover, despite the increase in mortality rate caused by a pandemic, the disruption in normal services (e.g. cancer care) actually results in reduced use of hospice and palliative care, which are known to protect against SGR.

Many bereaved FMs would appreciate bereavement support, and bereavement support has been identified as a clinical and research priority. Yet few acute or long-term care settings (where most death occurs in Canada) have devoted resources toward bereavement screening or support, so many FMs seek support from therapists or community-based bereavement groups outside of the public healthcare system.

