## **Phase 2: Prospective Bereavement Data Collection**

We will offer enrolment to the FM contacts indicated in the medical record of each patient who were identified in the retrospective chart review, beginning at minimum 6 months after the death of the patient. A list of FM contact names, phone number, and relationship to the deceased patient will be generated to all research assistants to contact FMs and offer study enrollment. For FMs who agree to enroll (our previous study found a 40-50% enrolment rate), we will collect basic demographic, mental health, and spirituality data similar to our previous work, as well as focused assessments of grief and relationships:

- The Brief Family Relationship Scale (BFRS) to determine closeness of FM to the deceased
- The Inventory for Complicated Grief-revised (ICG-r) to determine the severity of their grief symptoms. Those who enrol will complete the ICG-r at baseline (upon enrollment) and again 6-months later. A recent meta-analysis of psychological interventions for grief suggested that the ICG-r is superior to other grief measurement tools for measuring the effect of bereavement interventions.

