## **Phase 3: Virtual Support Groups**

FMs who participate in the prospective bereavement data collection (i.e. Phase 2) will be invited to attend a virtual support group (VSG) led by Bereaved Families of Ontario- Ottawa (BFO). In pre-COVID times, BFO presented monthly “*Support and Share*” nights with guest speakers, followed by breakout peer support groups for all different types of losses: loss of child, spouse, parent, loss by suicide, etc. These groups are facilitated by trained volunteers with a shared loss and include between 75 and 150 participants. These Support and Share Nights serve as intake sessions- interested participants from the breakout groups can attend “*Closed Groups*” where a smaller group of participants (up to 12) explore their grief more deeply. These run over 8-10 consecutive weeks with the same group of participants. They are led by trained facilitators who have experienced similar losses. Each week has a different theme, based on evidence-based components of bereavement support (e.g. writing a letter to the deceased). The sessions were put on hold in March by the pandemic, but

BFO plans to begin holding these *Closed Groups* by videoconference (these will be the VSGs) again in September 2020.

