### Phase 1-3: Quantitative Data Analysis

To address research objectives #1 and #2, we will divide the patients (and FMs) into three groups:

- a. Pre-COVID: Deaths that occurred in an acute care hospital before the impact of the pandemic was first felt in Ottawa (November 1st, 2019–February 29th, 2020): approximately 160 patients.
- b. COVID: Deaths that occurred in an acute care hospital due to COVID-19 (March 1st – August 31st, 2020). Approximately 250 COVID-19 deaths have been reported between January and June 2019 in Ottawa by Ottawa Public Health, of which preliminary data suggest approximately 80 patients died in acute care.
- c. Non-COVID: Deaths that occurred in an acute care hospital between March 1st – August 31st, 2020 but were not COVID-19 related: approximately 160 patients.

To assess the overall impact of the pandemic, we will perform statistical comparisons of clinical and end-of-life care metrics for the Pre-COVID vs. COVID and Non-COVID groups combined. Patients will be matched based on their health and demographic profiles in a 2:1:2 ratio (2 decedents in pre-COVID period: 1 decedent during the pandemic who died of COVID-19: 2 decedents who died during the pandemic of non-COVID-19 causes). We will compare the COVID vs. Non-COVID groups to determine how much of the impact was specifically associated with COVID infection as opposed to the pandemic in general. Pairwise comparisons will be performed using an unpaired t-test or Mann-Whitney test as appropriate for the distribution of the data. We will then also use logistic regression analysis to identify factors associated with an ICG score  $>25$  (i.e. severe scores).

To address research objective #3, we will compare the changes in ICG scores between baseline and 6-months post-baseline for FMs who did versus did not participate in the VSGs (i.e. the difference in differences). This comparison is important since grief symptoms typically improve over time even without intervention. In addition, group allocation is not random and so our analysis may be

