confounded by the possibility that people who choose to participate in support groups have more severe symptoms. We will therefore perform an adjusted analysis similar to Newsom et al. in their naturalistic controlled trial of community-based bereavement support. We will estimate an average score for the outcome variable at each time point for the support-group and no-support-group (control) conditions. Where baseline differences in clinical, demographic or loss-related variables exist, these variables will be added as covariates. Assumptions of linearity, multicollinearity, homoscedasticity, and normality of residuals will be tested prior to analysis.

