#### **Phase 4: Family Member Interviews**

To address research objectives #1 and #3, FMs who participated in a VSG will be invited to participate in semi-structured interviews to determine how the FM perceived their loved one's end-of-life experience, their own bereavement experience, the usefulness of the VSG, and successes and challenges of the intervention. Approximately 20 interviews will be conducted, or until thematic saturation is reached. We will use maximum variation sampling based on grief severity (ICG scores), participant demographics, and whether or not the participants loved one died of COVID-19 versus other causes.

Semi-structured interviews will also be conducted with bereaved family members who did not attend any VSGs. This will be done to better understand their loved one's end-of-life experience, their own bereavement experience, their experiences of facilitators or barriers to attending VSGs, their reasons for not attending the VSG, and how they coped overall with their loss (e.g., the use of other coping strategies).

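### Objective 3 compares VSG attenders with self-selected non-attenders, but no listed item or covariate records other or earlier bereavement support

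*Combined protocol and SAP*

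**What the plan says.** Under Phase 1-3: Quantitative Data Analysis, Objective 3 is a difference in differences: "we will compare the changes in ICG scores between baseline and 6-months post-baseline for FMs who did versus did not participate in the VSGs". The two arms of that comparison are called "support-group and no-support-group (control) conditions". The plan recognises that allocation is not random and that attenders may have more severe symptoms. Its remedy is: "Where baseline differences in clinical, demographic or loss-related variables exist, these variables will be added as covariates".

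Under Phase 2: Prospective Bereavement Data Collection, the data from FMs are described as follows: "we will collect basic demographic, mental health, and spirituality data similar to our previous work, as well as focused assessments of grief and relationships". The two instruments named are the Brief Family Relationship Scale and the ICG-r. The ICG-r is completed at enrolment, at least 6 months after the death, and again 6 months later.

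On other support, Background and Rationale says that few acute or long-term care settings have put resources into bereavement care, "so many FMs seek support from therapists or community-based bereavement groups outside of the public healthcare system". It adds that many community organisations were planning to move their groups online. Phase 3 provides for referral of FMs with concerning features to professional support. It also says of the in-person sessions at Bereaved Families of Ontario (BFO): "The sessions were put on hold in March by the pandemic".

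Phase 4 interviews with non-attenders will explore "how they coped overall with their loss (e.g., the use of other coping strategies").

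**The concern.** Attending a VSG is a help-seeking choice. People who make it may also be more likely to see a therapist or join another group. Equally, people who decline it may do so because they already have help elsewhere. Either pattern puts a second source of support unevenly across the two groups, and its effect on ICG change is then attributed to the VSG.

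The adjustment can use only variables that were collected, and support use is not among those listed. The Phase 4 interviews do not fill the gap. They cover a subset, they are qualitative, and the topics listed for attenders do not include other support, so the information would be one-sided.

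At stake is the sign and size of the preliminary efficacy estimate. The dissemination plan foresees extending the approach to other BFO chapters and partner organisations, so the estimate may be used. Support that is not asked about at the two planned contacts would be hard to recover later.

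**Working it through.** The plan gives no effect size, SD, alpha or power for Objective 3, so there is no design figure to reproduce. The check has two parts.

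**1. Is other support captured anywhere?**

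| Place in the protocol | What it contributes |
|---|---|
| Background and Rationale | Says that other support is sought and that further virtual groups are planned |
| Phase 3 | Refers some FMs to professional support; no data collected from VSG sessions |
| Phase 2 data list | Demographic, mental health and spirituality data, family relationship scale, ICG-r; no support item named |
| Covariate rule, Objective 3 | Baseline clinical, demographic and loss variables; support not named |
| Phase 4 | Other coping asked of interviewed non-attenders only |

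So no listed quantitative variable carries the information.

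**2. How large could the bias be?**

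Inputs from Study Participants: about 200 FMs, of whom 100 are expected in a VSG, leaving 200 − 100 = 100 non-attenders.

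Assumed inputs, none from the documents: SD of change 1, two-sided alpha 0.05, no dropout, and additive effects. Let d_VSG and d_other be the standardised improvements from the VSG and from other support, and let qV and qC be the shares of attenders and non-attenders who use other support. Then

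expected contrast = d_VSG + (qV − qC) × d_other.

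For scale, the smallest effect detectable at 80% power with 100 per group is (1.96 + 0.84) × √(2/100) ≈ 0.40.

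| d_VSG | d_other | qV | qC | Expected contrast | Power |
|---|---|---|---|---|---|
| 0.40 | 0.40 | 30% | 30% | 0.40 + 0 = 0.40 | 81% |
| 0.40 | 0.40 | 10% | 30% | 0.40 − 0.20 × 0.40 = 0.32 | 62% |
| 0.40 | 0.40 | 10% | 50% | 0.40 − 0.40 × 0.40 = 0.24 | 40% |
| 0.40 | 0.20 | 10% | 30% | 0.40 − 0.20 × 0.20 = 0.36 | 72% |
| 0.40 | 0.40 | 30% | 10% | 0.40 + 0.20 × 0.40 = 0.48 | 92% |
| 0 | 0.40 | 50% | 10% | 0 + 0.40 × 0.40 = 0.16 | 20% (false positive) |

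Under this model the bias depends on qV − qC and on d_other. It can have either sign, and it vanishes when use is equal.

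**Earlier support.** A stable shift in the ICG level from support before baseline cancels in the within-person difference. What remains is any influence of that support on later change, for example through less room to improve.

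**Choice of sensitivity analysis.** Removing users of other support from the non-attenders only would create a bias of its own. With d_VSG = d_other = 0.40 and qV = qC = 30%, the full comparison gives 0.40. Setting qC to 0 while qV stays at 30% gives 0.40 + 0.30 × 0.40 = 0.52, an inflation of 30%. The restriction must therefore apply to both groups.

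**The case against.** The strongest reply is that this is a naturalistic comparison of people who did and did not use a service offered as routine care. Comparing VSG attendance with whatever else people do is a legitimate question, and dilution by other support is a bias only against a no-support target, which the plan never states. That stands. A reader might infer from the control label that non-attenders are taken to have had no help at all. The wording can equally mean only that they were not in a VSG, so the label needs clarifying but does not show that stronger assumption.

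Second, the Phase 2 list is a summary and the questionnaire is not in the documents. The mental health data are only said to resemble the investigators' previous work, so a support item may exist. It can be said that none is listed, not that none will be asked.

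Third, a reader might infer serious carry-over from in-person BFO groups. The documents limit this. Those groups stopped in March 2020 and Phase 2 starts in October 2020, about seven months later. Closed groups ran 8-10 weeks, so few FMs bereaved early in 2020 could have completed one. Date of death is collected for subgroup and regression use and gives a proxy for access. Differencing removes a stable level effect.

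Fourth, the Background also says that in-person treatment is limited and that distancing rules out its use, and FMs told that their symptoms are severe are pointed to the VSGs, not elsewhere. So the extent of other support is unknown and may be small. This leaves the size open but does not remove the gap, since virtual alternatives and professional referral are in the plan's own text.

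Finally, Objective 3 claims only preliminary efficacy, and self-selection by severity is already acknowledged. That lowers the consequence, but adjusting for severity does not adjust for support use.

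**Conclusion.** The point holds as a gap in the listed data and analysis: the plan says that other bereavement support is sought and available, but names no quantitative item or covariate for it. If use differs between the groups, the VSG estimate is biased, and the listed data can show neither direction nor amount. In the illustrations an assumed effect of 0.40 becomes anything from 0.24 to 0.48, and a null effect becomes 0.16. All of these rest on assumed shares, assumed effectiveness and additivity, and equal use gives no bias under that model.

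It would go too far to say that the bias cannot be corrected. Recording support at the two planned contacts allows it to be described and partly adjusted for. This is a cheap improvement to a preliminary, non-randomised comparison, not a flaw that invalidates it.

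**What to change.** If the Phase 2 questionnaire already contains suitable items, name them in the protocol and bring them into the Objective 3 analysis. Otherwise:

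- **Baseline item:** any bereavement group, counselling or therapy since the death, including in-person BFO groups.
- **6-month item:** any such support since baseline, other than the VSG.
- **Label:** call the comparator *VSG non-attenders (usual support)*.
- **Model:** include pre-baseline support as a prespecified covariate, whether or not it differs at baseline.
- **Reporting:** tabulate post-baseline other support by group. Do not enter it as if it were a baseline covariate, because it may depend on VSG attendance and on symptoms.
- **Sensitivity analysis, if wanted:** restrict both attenders and non-attenders to those with no other formal support, and label the result exploratory for the same reason.

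The cost is about one minute per contact at contacts already planned, some changes to the analysis text, and smaller groups in the sensitivity analysis.

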All participants in the prospective bereavement data collection component of this study will be invited to participate in the VSGs (see approved Virtual Support Group Information Sheet), regardless of the severity of their symptoms. Those with severe symptoms (indicated by an ICG-r score  $>25$ ) will be notified that their symptoms are considered to be severe, with a suggestion to attend the VSGs. A recent meta-analysis of psychological interventions for grief found higher effect sizes in studies of participants who were  $>6$  months post-loss, and those with higher baseline symptom levels. However, no participant in our study will be randomized to any treatment assignment, and the decision to attend the VSG will be left to the FM. Family members will participate in the virtual support group as part of routine care available to them by BFO. The support group is not a study-specific intervention, nor will any research team members be involved in the administration of the virtual support group, and no data will be collected from the virtual support group online sessions. The scope of the research study related to the virtual support group is to a) inform the 200 bereaved family participants about the support group, so that they may seek out this care available to them and b) conduct qualitative interviews with 20 participants who attended the virtual support group (see Phase 4 below). As such, while we will obtain consent for conducting the Phase 2 questionnaires and the Phase 4 qualitative interviews, consent will not be obtained for participation in the virtual support groups. Any participant who expresses suicidal ideation or intention, or other concerning features of severe grief reaction, will be referred for urgent assessment and professional support through their family physician or the emergency department, as per usual practice with BFO.

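### Objective #3 plans one average VSG contrast across all grief severities, so any effect in family members with severe grief cannot be read from the planned result

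*Combined protocol and SAP*

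**What the plan says.** The Phase 3 section opens the VSG to everyone in the prospective component: "All participants in the prospective bereavement data collection component of this study will be invited to participate in the VSGs", "regardless of the severity of their symptoms". FMs scoring above 25 on the ICG-r "will be notified that their symptoms are considered to be severe, with a suggestion to attend the VSGs". The same paragraph cites a meta-analysis of psychological interventions for grief in which effect sizes were higher in studies of people more than six months after the loss "and those with higher baseline symptom levels".

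The quantitative analysis section then says for Objective #3 that "we will compare the changes in ICG scores between baseline and 6-months post-baseline for FMs who did versus did not participate in the VSGs". The form of the estimate is: "We will estimate an average score for the outcome variable at each time point for the support-group and no-support-group (control) conditions". The covariate rule is: "Where baseline differences in clinical, demographic or loss-related variables exist, these variables will be added as covariates". The section recognises that people who choose the VSG may have more severe symptoms, and treats this as confounding.

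Severity has other uses in the plan, but none gives a VSG effect by severity. ICG >25 is the outcome of the logistic regression for risk factors. ICG scores guide the sampling of interviewees in Phase 4. The sub-group analysis mentioned under Phase 1 Data Collection concerns chart-review variables.

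**The concern.** The plan names baseline severity as something that may change how well grief interventions work, then averages over it. A covariate added because the groups differ at baseline corrects imbalance. It still returns one coefficient and does not let the effect vary with severity.

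That single figure depends on the severity mix of the FMs who happen to enrol and attend, so it does not carry over to a group with another mix. The study is about severe grief reactions, and its Significance section speaks of prioritising those in greatest need. A null average could be taken to mean that VSGs do not help severe-grief FMs, which the analysis would not have examined. A severity result produced afterwards would be post hoc.

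**Working it through.** **Inputs from the documents.** About 200 FMs, of whom about 100 are expected to attend a VSG (Study Participants); severity cut-off ICG-r >25 (Phase 3). No SD, effect size, alpha or power is stated for Objective #3, so there is no planned figure to reproduce.

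**Assumptions.** 30-50% of the 200 FMs are above 25, and 60-70% of those attend. The VSG benefit is 5 points in severe FMs and 0 in others, with change SD 10 and two-sided 5%. There is no attrition.

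**1. What a severity-adjusted average would show.** With severity (>25 or not) as a main-effect covariate, each stratum has weight w = n1·n0/(n1 + n0), where n1 and n0 are its attenders and non-attenders. The average is 5 × wS/(wS + wN), with S severe and N other. The severe-group SE is 10/√wS, the interaction SE is 10 × √(1/wS + 1/wN), and power is Φ(5/SE − 1.96).

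| Severe att./non-att. | Other att./non-att. | wS | wN | Adjusted average | Severe-group SE | Power, severe only | Interaction SE | Interaction power |
|---|---|---|---|---|---|---|---|---|
| 36/24 | 64/76 | 14.4 | 34.7 | 1.47 | 2.64 | 47% | 3.13 | 36% |
| 42/18 | 58/82 | 12.6 | 34.0 | 1.35 | 2.82 | 43% | 3.30 | 33% |
| 56/24 | 44/76 | 16.8 | 27.9 | 1.88 | 2.44 | 54% | 3.09 | 37% |
| 60/40 | 40/60 | 24.0 | 24.0 | 2.50 | 2.04 | 69% | 2.89 | 41% |
| 70/30 | 30/70 | 21.0 | 21.0 | 2.50 | 2.18 | 63% | 3.09 | 37% |

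The average is 27-50% of the severe-group effect. For example, for 42/18: 42×18/60 = 12.6; 58×82/140 = 34.0; 5 × 12.6/46.6 = 1.35.

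**2. A milder pattern.** If other FMs gain 2 points, the average is 2 + 3 × wS/(wS + wN), which runs from 2.81 to 3.50 (56-70% of 5). If the benefit is the same at every severity, there is no dilution.

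**3. What a change contrast without baseline ICG-r would show.** Assume baseline ICG-r is normal with mean 20 and SD 14, which puts 36% above 25, and a baseline to follow-up correlation r of 0.6-0.8. Mean baseline is then 34.5 in severe FMs and 11.8 in others, a gap of 22.7. With no VSG effect at all, the expected false benefit is (1 − r) × (difference in mean baseline between attenders and non-attenders).

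- Attendance 70% of severe and 40% of others: the severe share is 0.497 among attenders and 0.220 among non-attenders. The baseline difference is 0.277 × 22.7 = 6.3, and the false benefit is 1.3 (r = 0.8) to 2.5 (r = 0.6).
- Attendance 80% and 30%: the shares are 0.601 and 0.139. The baseline difference is 10.5, and the false benefit is 2.1 to 4.2.

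With a true benefit of 5 points in severe FMs and 0 in others, add 5 × the severe share of attenders (2.5 or 3.0). The contrast becomes 3.7 to 7.2 points. A simulation with 1,000,000 FMs per scenario gave the same ranges (false benefit 1.2-4.2; 3.7-7.2 with the true effect). With baseline ICG-r in the model it gave about 0 with no true effect and 2.0-2.2 points with it.

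**The case against.** A reader might infer that the planned result must understate or hide the effect in severe FMs. The documents do not support that, for three reasons.

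- Direction: the plan expects attenders to be more severe and encourages FMs above 25 to attend. A change contrast that omits baseline ICG-r is then pushed towards benefit and can exceed the severe-group effect (step 3). Dilution follows once baseline severity is adjusted for, and the covariate rule leaves open whether it will be.
- Premise: as worded, the cited pattern compares studies of psychological interventions. It does not show that individuals within a volunteer-led peer group respond differently by baseline score, and no size is given.
- The 5-against-0 case is the extreme one. Dilution shrinks if other FMs also benefit and vanishes if the effect is uniform.

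It is also fair to say that the all-comers average is a legitimate quantity for a service open to everyone, that Objective #3 asks only for preliminary efficacy, and that interaction power is poor. These points limit how the severity result may be used. They do not answer the omission: no planned output shows what happens in severe-grief FMs, and adjusting for severity as a confounder does not supply it.

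**Conclusion.** The point holds as an omission whose direction of error is not fixed. The plan gives one average contrast, and any VSG effect in FMs with ICG-r >25 cannot be read from it. If the cited pattern carries over to VSGs, a baseline-adjusted average is diluted: 1.35-2.5 points against an assumed 5 in severe FMs and 0 in others, less so if others gain too. If baseline ICG-r is left out, regression to the mean can make the contrast too favourable, by about 1.2-4.2 points under the assumptions shown. All these sizes rest on assumed effects, SD, correlation and attendance. The conclusion that the severe-group effect is not estimated rests on the text alone. This is an inexpensive improvement, and the overall average remains valid as one of the reported quantities.

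**What to change.** In the Objective #3 analysis text:

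1. Name baseline ICG-r, as a continuous score, as a covariate in every case, and add a VSG-by-baseline ICG-r term.
2. Keep the overall average VSG effect.
3. Beside it, report the estimated VSG effect with 95% CI for FMs with baseline ICG-r >25.
4. Tabulate attenders and non-attenders by baseline ICG-r range, so that no effect is read where one group is nearly empty.
5. Label the severity-specific result exploratory, and interpret it from the estimate and interval, not from an interaction p-value.

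**Cost.** SAP wording, one extra model term and one table. No new data are needed, since the ICG-r is already collected at baseline and six months later. The downside is imprecision. With about 100 v 100 FMs and change SD 10, the severe-group SE is about 2.0-2.8 points, so the 95% CI is about ±4.0 to ±5.5 (1.96 × 2.04 and 1.96 × 2.82), and attrition would widen it. Interaction power for a 5-point difference is only about 33-41%. The estimate also remains non-randomised, so unmeasured reasons for attending can still bias it.

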## TIMELINE

Month	2020				2021										
	S	O	N	D	J	F	M	A	M	J	J	A	S	O	
Ethics Approval (September-November 2020)															
Phase I: Retrospective chart review (Quantitative- October 2020 – February 2021)															
Phase II: Prospective Bereavement Data Collection (Quantitative- October-December 2020, April-June 2021)															
Phase III: Virtual Support Groups (October 2020 – March 2021)															
Quantitative Data Analysis (June – August 2021)															
Phase IV: FM Interviews (November 2020 – June 2021)															
Qualitative Data Analysis (January - August 2021)															
Knowledge Translation and Dissemination (August -October 2021)															

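### The Objective 3 comparison groups family members by a choice made during follow-up, so the VSG effect is open to bias of unknown net direction that baseline covariates cannot remove

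*Combined protocol and SAP*

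**What the plan says.** The analysis section (Phase 1-3: Quantitative Data Analysis) sets the Objective 3 contrast: "we will compare the changes in ICG scores between baseline and 6-months post-baseline for FMs who did versus did not participate in the VSGs". It calls this a difference in differences and justifies the comparison group on the ground that "grief symptoms typically improve over time even without intervention". It accepts that allocation is not random and that people with worse symptoms may be the ones who attend. Its answer is an adjusted analysis: "Where baseline differences in clinical, demographic or loss-related variables exist, these variables will be added as covariates".

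Under Phase 3, every enrolled FM is invited and "the decision to attend the VSG will be left to the FM". Those with an ICG-r above 25 "will be notified that their symptoms are considered to be severe, with a suggestion to attend the VSGs". Closed groups last 8-10 weeks, and the study takes no data from the sessions. Under Phase 2, "Those who enrol will complete the ICG-r at baseline (upon enrollment) and again 6-months later", so there is no score at the time of joining.

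The Timeline gives "Phase II: Prospective Bereavement Data Collection (Quantitative- October-December 2020, April-June 2021" for the two questionnaire rounds, and its entry "Phase III: Virtual Support Groups (October 2020" continues to March 2021. No section states a joining deadline, a minimum attendance, or how to classify an FM who joins late.

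**The concern.** The comparison group is meant to show how grief changes without the VSG. As written, it consists of FMs who had still not taken part when follow-up ended. That status is settled after baseline, within the same six months over which the change is measured.

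If an FM whose grief eases early sees no need to join, and one whose grief persists joins in January, the comparison group keeps the good courses and the VSG group collects the poor ones. If instead those who are recovering find the energy to join, the selection runs the other way. In either case the selection acts on something that happens after baseline, and a baseline covariate can correct only for what it predicts of that later course.

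At stake is the preliminary-efficacy part of Objective 3. A null, harmful or beneficial result could each arise from who joined and when.

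**Working it through.** The documents give no power calculation, SD or effect size for Objective 3, so there is no planned figure to reproduce. Two things can be checked: whether late joining is possible on the plan's dates, and what it could do to the estimate.

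**1. Dates (from the Timeline and Phase 3)**

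Last start of a full course = 31 March 2021 minus course length.
- 10 weeks (70 days): 20 January 2021.
- 8 weeks (56 days): 3 February 2021.

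Days from baseline to that last start:

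| Baseline | 10-week course | 8-week course |
|---|---|---|
| 1 October 2020 | 111 | 125 |
| 15 November 2020 | 66 | 80 |
| 31 December 2020 | 20 | 34 |

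Follow-up is about 182 days, so for the earliest enrollers joining is possible for 111/182 = 61% to 125/182 = 69% of it. If a single session counts as participation, which the plan does not exclude, the window extends to the end of March.

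**2. Simulation in SD units**

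From the plan: 200 FMs, about 100 attending. Assumed: no true effect; autoregressive latent grief with 6-month correlation 0.6-0.8; reliability 0.9; odds of joining 1.5-3 times higher per SD of current grief at each half-monthly decision. Positive means the VSG looks worse.

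- Ever/never grouping, joining possible for 2.5 months, 6-month score regressed on group and baseline score (ANCOVA): bias about +0.08 to +0.26 SD, with 9-45% rejection at a nominal 5%.
- Same data, unadjusted change (6 months minus baseline): bias about -0.06 to -0.26 SD, with 9-43% rejection. Joiners start higher and regress towards the mean.
- Group fixed at baseline, ANCOVA: +0.02 to +0.09 SD, with about 4-13% rejection.

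At correlation 0.7 and odds ratio 2, the first two give about +0.15 SD and -0.14 SD. The sign turns on whether baseline ICG-r is in the model.

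**3. Simulation in ICG points**

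Assumed: baseline mean 22, SD 12; measurement-error SD 4; mean improvement 4, SD 6 between FMs; about 36% joining early; n = 200; 2,000 runs per scenario.

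| Scenario, no true effect | ANCOVA ever/never | Unadjusted change |
|---|---|---|
| No late joining | 0.0 | -0.6 |
| Late joining unrelated to course (13% of FMs) | 0.0 | -0.7 |
| Late joining driven by persisting grief (9-22%) | +1.3 to +4.0 | +0.5 to +3.1 |
| Late joiners already improving | -1.2 | -1.8 |
| Persisting grief drives late joining and early joiners have a better prognosis (weak to strong) | +1.5, +0.5, -1.1 | +0.7, -0.2, -1.7 |

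In the third row, a falsely significant result against the VSG appears in 19-91% of runs. With a true 3-point benefit, the ANCOVA ever/never estimate under persisting-grief joining falls to between 1.7 and 0.0.

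In this model even the unadjusted change can err against the VSG, so neither estimator has a fixed direction of error.

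**4. Exposure fixed at baseline, late joiners kept in the no-VSG group**

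With no true effect and early joining unrelated to later course, bias is -0.07 to +0.04 points and false harm 2.4-3.3% (nominal 2.5%). A true 3-point benefit is diluted to 1.9-2.3 when 13-21% join late. If early joiners would have improved more anyway, bias is -1.5 to -5.0 points, in favour of the VSG.

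**The case against.** A reader might infer that the plan's estimate is biased against the VSG in a predictable direction. The documents do not support that, for three reasons.

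- **The estimator is unsettled.** The analysis section describes a comparison of changes and never names baseline ICG-r as a covariate. In the first model the unadjusted comparison errs in favour of the VSG.
- **Nothing is given on how many FMs join late, when, or why.** The Background suggests that distancing rules may reinforce avoidance, and Phase 4 plans interviews about barriers to attending. FMs with persisting grief may therefore stay out, which would worsen the comparison group.
- **Motivated early joiners may have a better prognosis**, which also favours the VSG.

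It can also be said that late joining is limited. Closed groups keep the same members, and the invitation comes at enrolment, with a prompt for severe scorers, so early joining may dominate. If 40% join at invitation and only 10% later (an assumption; correlation 0.7, 2.5 months), the ANCOVA bias falls to +0.05 to +0.14 SD, with 6-21% rejection. FMs of patients who died in July or August 2020 cannot be approached before January or February 2021, so they have little or no room to join a full course late.

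Finally, this is a declared natural experiment seeking preliminary efficacy, and the plan already acknowledges non-random allocation.

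These arguments dispose of any claimed direction and reduce the likely size. They do not remove the defect: the plan acknowledges only severity at entry, offers only baseline covariates, and does not provide for recording when anyone joined. Proportion argues for a cheap remedy rather than for none.

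**Conclusion.** The concern holds as one of openness to bias. Exposure can be chosen during the interval over which change is measured, no joining window is stated, and covariates chosen for baseline differences cannot remove selection on the later course of grief.

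The net direction is unknown. It is against the VSG if persisting grief prompts late joining and baseline ICG-r is adjusted for. It can favour the VSG in an unadjusted change-score comparison, through regression to the mean, or if early joiners have a better prognosis.

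The size could matter: roughly a quarter of an SD either way at the top of the first simulation, and near zero if late joining is rare or unrelated to the course of grief. The possibility of late joining comes from the documents; the magnitudes rest on assumed joining rates, odds ratios, correlations and SDs.

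Replacing the planned contrast outright with one based on acceptance at baseline is not justified either. That changes the question, dilutes the effect and leaves early self-selection in place. Reporting both is the defensible course.

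**What to change.** 1. Include baseline ICG-r as a covariate in the Objective 3 model in every case, not only where a baseline difference appears.
2. At the baseline contact, record whether the FM accepts the VSG invitation. At the 6-month contact, ask for the date of the first session and the number of sessions attended. These must be self-reported, because no session data are collected.
3. Beside the planned ever/never contrast, pre-specify an analysis with exposure fixed at baseline (accepted, or joined within a short stated window) that keeps later joiners in the no-VSG group. Interpret preliminary efficacy from both.
4. State that the ever/never contrast is open to selection on the course of grief after baseline, without asserting a direction.

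Cost: two or three questions in calls already made, one extra model and a few lines of analysis text. The baseline-fixed contrast is diluted by late joiners and by acceptors who never attend, and it does not remove early self-selection. Both limits should be stated with the results.
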